5.0 RISKS & BENEFITS

Study 1 Risks

- Exercise Task:
 - Some participants may find it difficult to complete the exercise portion of the task. Individuals who have been advised not to exercise by a doctor are excluded from participating in the study. Participants will be told they can stop at any time if they are feeling ill from exercise. Additionally, participant’s perceived exertion will be measured to ensure they are not at their maximum exertion for too long. In extreme cases, participants may experience cardiac problems associated with exercise. There is a defibrillator in the building where exercise testing will occur. Participants who meet eligibility criteria will be required to perform a sub-maximal exercise test. The participants will likely experience muscle soreness in their legs for between 24 to 48 h after exercise. This soreness is completely normal, and as these individuals will be inexperienced exercisers, they will receive ample warning regarding the risk.
 - Muscle strains or pulls resulting from the exercise testing sessions are also possible. However, prior to and during each exercise session, the participants will be familiarized with the exercise protocol and the correct technique required to perform the exercise safely on the treadmill. Therefore, we aim to minimize potential injury through proper instruction and protocol familiarization.
 - Trained, non-physician exercise physiologists certified in CPR will supervise participants undergoing testing and assessments. An automated electronic defibrillator (AED) is located in the Baylor Science Building and no less than two researchers will work with each participant during testing sessions. In the event of an emergency, one researcher will check for vital signs and begin intervention if required, while the other researcher contacts Baylor’s campus police at [name]. All emergency procedures are posted above the phones in the event any other research investigator(s) is at hand to provide assistance.
- Stress Task:
 - The risks associated with the acute psychological stress task are minimal. The paradigm being used has been tested on thousands of people and no adverse side effects, other than feeling stressed during the task, have been experienced.
- functional Magnetic Resonance Imaging (fMRI):
 - There are some inherent risks associated with MRI in regard to metal implants. Entering the scanner with metal can cause risk to the machine and the participants.
 - We will ensure that all participants undergo a thorough screen to determine eligibility for the fMRI. Participants who have metal within them such as: aneurysm clips or pacemakers, will be excluded. There are known dangers from MRI to people with heart pacemakers, with the possibility that the pacemaker may malfunction, as well to people with metal implanted devices such as aneurysm clips that might be moved in a dangerous manner.
 - Participants will be asked questions about metal exposure throughout their lifetime and will be screened

- with a metal detector to make sure they have not left any metal on their person.
- There are no known effects of the magnetism or radio waves used in MRI.
- Some people may become claustrophobic while in the machine. Should this occur, the examination will end and they will be quickly removed from the scanner. This is an occasional negative event that is usually mild in severity and quickly resolved upon leaving the scanner.
- Electrocardiography
 - Electrocardiography (ECG) carries minimal risk. However, some individuals may have skin irritation or an allergic reaction from the electrodes (sticky pads) being used. If you find the sticky pads are causing too much irritation, please let the researcher know and they can be removed.
- Loss of Confidentiality
 - A risk of taking part in this study is the possibility of a loss of confidentiality. Loss of confidentiality includes having your personal information shared with someone who is not on the study team and was not supposed to see or know about your information. The researcher plans to protect the participants' confidentiality through standard procedures noted in this form.

Incidental Findings:

- While the testing procedures the participants will undergo during this study are for research purposes only, there is the possibility the researchers may note a result potentially important to the participant's health. In this event, the participant in question will be contacted to explain the observation. If they do not have a private physician, we will refer them to an appropriate clinic for follow-up. Proceeding with any additional tests and/or treatments, if required, will be left to their discretion, and the participant or their insurance company will be responsible for any costs incurred.

Benefits:

- Possible benefits include participants learning a little bit more about themselves and how they cope with stress.
- Participants will be made aware of the proposed benefits of the study. All benefits will receive a copy of their personal results, which include: height, weight, BMI, and level of cardiovascular fitness. Participants will also have the opportunity to receive a printed picture of an image of their brain from the structural scan.
- Others may benefit in the future from the information that is learned in this study. Information from this study may be used to develop interventions to help people cope with stress.

6.0 STATISTICAL ANALYSIS

All participants will receive a unique ID for the study. IDs will be given starting with the number 9000. Questionnaire data will be collected through the Qualtrics survey system using tablets in the laboratory. Qualtrics will store the data on an encrypted server that will only be accessed by the Co-Investigator, primary RA, and students working on the study.

Analytic plan: Averages of the main study variables will be calculated for the main analyses of examining cardiovascular, metabolic, and neural activity at rest and during the acute psychological stress task. Reactivity will be calculated as: Stress activity – Baseline activity. fMRI data will be preprocessed and analyzed with statistical parametric mapping software (SPM12; <http://www.fil.ion.ucl.ac.uk/spm>) using established realignment, co-registration, smoothing, and motion correction analyses³⁸. Stressor-evoked brain activation will be determined by comparing the BOLD signal activity during the incongruent (stress) versus congruent (control) condition^{9,38}. For the analyses between stressor-evoked cardiovascular activity and stressor-evoked neural activity, machine learning techniques will be used to generate a multivariate pattern (3D regression weight map) that relates to heart rate and metabolic responses to stress. The study will then test if this generated multivariate pattern can reliably predict cardiovascular and metabolic responses to stress. Recent papers examining brain multivariate pattern prediction of cardiovascular responses to stress found the between subjects correlations to be relatively small, $r = \sim .20$. Based on these results, with alpha set at .05 and power = .80, it is estimated we will need a sample of at least $N = 140$.

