Autonomic responses to stress and future cardiovascular disease risk. There is longstanding and cumulative epidemiological evidence that individuals who exhibit a phenotype characterized by the expression of large-magnitude cardiovascular reactions are at elevated risk for clinical and preclinical endpoints of CVD⁵⁻⁸. My work and the work of others demonstrates that individual differences in these responses are relatively stable⁹⁻¹³. Moreover, cardiovascular responses during acute psychological stress, stress that does not require physical exertion, can be metabolically inappropriate—meaning that the cardiovascular system is working in excess of metabolic demand¹⁴⁻²⁴. To determine if cardiovascular responses are metabolically appropriate, we measure oxygen consumption (marker for metabolic activity) and cardiovascular activity at rest and during a graded exercise test. The cardiovascular and metabolic responses to moderate exercise is a marker for metabolically appropriate heart rate changes¹⁴. Individual regressions of oxygen consumption on heart rate are calculated based on measurements during exercise. The computed regressions for each participant are then used with their oxygen consumption scores recorded during stress to “predict” what their heart rate should be during baseline and acute psychological stress. The difference between observed heart rate and predicted heart rate is called additional heart rate, which represents heart rate in excess of metabolic demand (i.e., the degree to which the heart is responding inappropriately or in excess during psychological stress). Figure 2 displays a representation of predicted heart rate versus actual heart rate during a standard psychological stress testing paradigm¹⁴. The lack of physical exertion during psychological stress does not perturb the metabolic system, which results in predicted heart rate being the same as rest. However, participants, on average, demonstrate an increase in heart rate in excess of the metabolic demand. A longstanding view is that the repeated and cumulative expression of such metabolically-disproportionate, stressor-evoked, cardiovascular reactions contribute to, or exacerbate, pathophysiological changes that are conducive to CVD and CVD events among vulnerable individuals¹⁴⁻¹⁷. Recently, it has been proposed that the brain generates anticipatory visceromotor commands to alter cardiovascular physiology to prepare individuals to cope with psychological stressors²⁵ and that these commands are “visceral predictions”, insofar as to anticipate behavioral demands engendered by appraised stressors^{26,27}. Individuals with metabolically disproportionate responses may be displaying visceral prediction errors²⁸. The proposed work is both conceptual and empirical and provides a rationale for examining, in the context of CVD risk, the relationship between brain systems for visceral control and body metabolically exaggerated responses to stress.

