4.0 RESEARCH DESIGN, METHODS, AND STUDY ACTIVITIES

Rationale: Previous research has identified areas of the brain associated with psychological stress and cardiovascular responses to stress; however, this research has not examined what is thought to be the most detrimental responses to stress, known as metabolically exaggerated²⁸. Participants will have their metabolic and cardiovascular responses to stress measured, as well as undergo an fMRI scan to examine their stressor-evoked neural responses. The hypothesis here is that a multivariate pattern of stressor-evoked responses will be able to predict the magnitude to which cardiovascular responses to stress are excessive of metabolic demand and that this pattern will encompass areas implicated in stress processing and cardiovascular control. This aim will be vital in elucidating the neurophysiological pathways of metabolically excessive cardiovascular responses to stress by identifying key brain areas that are related to the peripheral responses.

Design: The protocol will be the same for all participants.

Duration: Visit 1 will take approximately 2 hours and Visit 2 will take approximately 2 hours. The total commitment will be 4 hours.

Visit 1 Protocol: Visit 1 is designed to determine the additional heart rate (i.e., degree to which each participant's response to stress is metabolically inappropriate). Participants will come to the laboratory to engage in a standard stress testing paradigm. Following instrumentation with cardiovascular equipment and body metabolic measuring equipment, participants will be given 20 minutes to adapt to the laboratory environment. This will be followed by a 10-minute formal resting baseline, and 18-minutes of acute psychological stress tasks (MSIT and Stroop task), see description below⁹. This will then be followed by four 4-minute bouts of cycling exercise incrementally increasing in demand¹⁴ and will include with a maximal exercise test (described below). Participants will fill out questionnaires regarding demographics and health behaviors.

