Visit 1 Measurements: Cardiovascular activity will be measured continuously⁴³ throughout the protocol using electrocardiogram and will be calculated for each minute of the protocol using Mindware Kubios processing software³⁴. Body metabolic rate, indexed by oxygen consumption, will be measured on a breath-by-breath basis assessing ventilation and analyzing inspired and expired gas composition using an integrated system. Metabolic rate will then be averaged for each minute. Additional heart rate will be calculated by first computing individual regressions of oxygen consumption on heart rate using data from rest and each of the 4-minute bouts of the graded exercise test¹⁴. The computed regressions for each participant will then be used, with each individual's observed oxygen consumption recorded during stress, to "predict" what heart rate should be during baseline and during the MSIT (acute psychological stress). The difference between observed heart rate and predicted heart rate will be additional heart rate, which represents heart rate in excess of body metabolic demand.

Visit 2 Protocol: Visit 2 is designed to measure stressor-evoked neural activity, required to develop multivariate analyses to predict metabolically excessive responses (i.e., additional heart rate). The same 150 participants will come to the VINS 17 CoE to engage in a functional magnetic resonance imaging protocol. The protocol will consist of a structural scan, followed by a functional scan during which participants will engage in the MSIT and Stroop.

Visit 2 Measurements: Functional and structural images will be obtained on a Philips Ingenia 3.0 Tesla Omega MRI scanner equipped with a 32-channel head coil. Blood-oxygen level-dependent (BOLD) images will be acquired over the stressor

[figure not shown]
period with the following parameters: FOV = 205 x 205 mm², matrix size = 64 x 64 mm², TR = 2,000 ms, TE = 28 ms, and FA = 90°. Functional scans will be obtained at rest and during an acute psychological stress task (MSIT).

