 - BMI: BMI will be determined from weight and height, where BMI equals weight (kg) / height (m^2). All BMI results will be recorded to the nearest 0.1 kg/ m^2 .
 - Waist circumference: Since waist circumference is positively correlated with abdominal fat content, this will be used as an adjunct marker of obesity for recruitment purposes. When standing at the participant's right side, a measuring tape will be extended parallel to the floor around the waist at the uppermost border of the right iliac crest. The measurement will be read to the nearest 0.1 cm at the end of the participant's normal expiration. A minimum of 2 measurements will be taken; however, if these vary by more than 2 mm a third measurement will be performed. Participants will also be given the option to place the tape measure around their own waist and hip for measurements if they would feel more comfortable. Every effort will be made to ensure male participants will have this measured by male RAs and female participants by female RAs. The participant is always given the option to take their own measurements with instructions from the RAs. There are always two RAs present during testing and the participant has the measurements taken in a private room (i.e., with two RAs and no other participants).
- Participants will also fill out questionnaires regarding demographics and health behaviors.

Procedures for the Second Laboratory Visit:

- Experimenters will greet participants as they enter the lab and lead them to the lab waiting room.
- Experimenters will walk the participants through the protocol of what will happen during the visit and give participants the opportunity to ask any questions they may not have asked during the first visit.
- Experimenters will then explain to participants the importance of removing any metal on their body and give them the opportunity to go into the changing room and remove any clothing with metal. Extra clothes without metal (basketball shorts and large t-shirts will be available if participants need them).
- Participants will then be walked into the scanning room and set-up for the scanning. The experimenter will ensure that the participant feels safe and comfortable in the scanning environment. If, for any reason, the participant appears to be becoming claustrophobic, they will be removed.
- Participants will be fitted with a blood pressure monitor and pulse oximeter to measure cardiovascular activity.

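### Section 6.0 states no cardiac or respiratory noise handling for the brain images and no check for it, although the predicted outcome is heart-rate based, so physiological signal could contribute to a positive result.

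*Combined protocol and SAP*

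**What the plan says.** **Preparation of the images.** Section 6.0 (Analytic plan) says the fMRI data will be handled in SPM12 "using established realignment, co-registration, smoothing, and motion correction analyses", citing an earlier study of brain patterns and stressor-evoked blood pressure.

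**Brain measure.** Stressor-evoked activation comes from "comparing the BOLD signal activity during the incongruent (stress) versus congruent (control) condition".

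**Target.** Machine learning will produce "a multivariate pattern (3D regression weight map) that relates to heart rate and metabolic responses to stress", and the study then tests whether that pattern predicts the responses. Section 4.0 is more specific about the target: "Visit 1 is designed to determine the additional heart rate", while "Visit 2 is designed to measure stressor-evoked neural activity, required to develop multivariate analyses to predict metabolically excessive responses". Additional heart rate is observed heart rate minus the heart rate predicted from oxygen consumption.

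**Recording in the scanner.** Section 4.0, Procedures for the Second Laboratory Visit: "Participants will be fitted with a blood pressure monitor and pulse oximeter to measure cardiovascular activity". No use of these readings in the fMRI model is stated, and no respiration recording in the scanner is named.

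**Link between visits.** Section 1.0 says that "individual differences in these responses are relatively stable". Section 4.0 (Acute psychological stress tests) reports strong test-retest reliability in pilot work for the excess heart-rate response to the MSIT. The MSIT, with the same social-evaluation deception, is used at both visits.

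**The concern.** BOLD is a blood-based signal. Pulsation, heart-rate change and breathing can alter it without any change in neural activity. In many fMRI studies this is mostly noise. Here the outcome is itself cardiac, so the same physiology may be correlated with the thing being predicted.

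The possible route has two links. Someone whose heart rate or breathing responds more to the incongruent condition in the scanner may show a larger physiological component in the contrast map. If reactivity is stable, that person also tends to have a larger response at Visit 1. A pattern fitted to the maps can use that component.

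Cross-validation, which Section 1.0 favours, would not expose this. An artefact that follows a stable trait also predicts in people left out of the training set. The problem is one of validity, not overfitting.

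What is at stake is interpretation. Section 4.0 expects the pattern to clarify neurophysiological pathways, and Section 1.0 presents the study as a test of visceral prediction errors. Both readings need the predictive signal to be neural.

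**Working it through.** **Step 1. What the listed steps remove.** Realignment and motion correction deal with head movement. Co-registration aligns images, and smoothing averages neighbouring voxels; neither models cardiac or respiratory signal. Section 4.0 gives TR = 2,000 ms, so sampling is at 0.5 Hz and anything above 0.25 Hz folds to a lower frequency. An assumed pulse of 70 per minute (1.167 Hz) folds to |1.167 − 2 × 0.5| = 0.167 Hz, inside the sampled band. Realignment does not remove it.

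**Step 2. The plan's own figures.** Section 6.0 plans on r of about .20 (cited work "found the between subjects correlations to be relatively small"), alpha .05, power .80 and N = 140. By Fisher z, N = ((z_alpha + z_power)/atanh(r))² + 3. For r = .20 this gives 194 two-sided or 154 one-sided, so 140 is not reproduced. That is a separate matter. What counts here is that the planned effect is small: .20² = 4% of variance.

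**Step 3. Size of an artefact-only correlation.** Let a be the correlation of the pattern score with the in-scanner physiological response, and b the correlation of that response with the Visit 1 outcome. With no neural relation, r = a × b. The documents give neither a nor b. Assumed ranges: a from .1 to .5, b from .2 to .4.

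**Step 4. Chance of significance.** At N = 140, two-sided .05:

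P = Φ(atanh(r)·√137 − 1.960) + Φ(−atanh(r)·√137 − 1.960), with √137 = 11.705.

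- r = .02: 0.0200 × 11.705 = 0.234; P = Φ(−1.726) + Φ(−2.194) = .042 + .014 = .056.
- r = .20: 0.2027 × 11.705 = 2.373; P = Φ(0.413) = .660, the second term being negligible.

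| a | b | r = a × b | P(significant) |
|---|---|---|---|
| .1 | .2 | .02 | 6% |
| .2 | .4 | .08 | 16% |
| .3 | .3 | .09 | 18% |
| .3 | .4 | .12 | 29% |
| .5 | .3 | .15 | 42% |
| .5 | .4 | .20 | 66% |

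The nominal figure is 5%. The range runs from close to nominal up to a correlation as large as the whole planned effect.

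**Step 5. What adjustment would show.** If the observed r is .20, the partial correlation given the scanner response is (.20 − ab)/√((1 − a²)(1 − b²)):

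- a = .1, b = .2: .18/√(.99 × .96) = .18.
- a = .3, b = .3: .11/.91 = .12.
- a = .5, b = .4: .00.

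Reporting the association before and after adjustment would therefore be informative across the assumed range.

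**The case against.** Several points on the other side are sound.

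- **The pipeline is partly cited.** A reader might infer that the images are corrected for head movement and nothing else. The documents do not support that. They show only that no physiological step is stated; whether the cited study used one cannot be seen. If it did, part of the remedy is one explicit sentence.
- **The route is indirect.** The main target is an oxygen-adjusted residual from another session, outside the scanner. The stability statement carries no coefficient and the pilot reliability claim no figure; neither is said to come from the scanner. This weakens the path without closing it. Section 6.0 also does not say which visit supplies the heart-rate response; Visit 2 readings would make the path same-session and stronger.
- **The contrast cancels shared physiology.** The congruent task uses the same button presses, so only a differential response survives. One cannot conclude that the map does contain an outcome-linked artefact, only that it can: Section 4.0 describes the incongruent condition as the stress-inducing one.
- **The check remains possible later.** A reader might infer that the study could never tell artefact from neural signal. That goes too far: the images allow it, a pulse oximeter is fitted, and Section 7.0 keeps data indefinitely. What is missing is prespecification.
- **Correction can remove real signal.** Brain activity that drives heart rate is correlated with heart rate. This argues against making noise removal the primary analysis, not against a sensitivity analysis.

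**Conclusion.** The gap holds as an unaddressed alternative explanation. No section states cardiac or respiratory noise handling or a check for it. Because the target is cardiac, the task is shared and reactivity is taken to be stable, a non-neural contribution to a positive result is plausible, and the planned test would not separate it.

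The size cannot be derived from the documents. The 6% to 66% range depends wholly on the assumed a and b and on a two-sided test, since Section 6.0 does not state sidedness. It should not be read as the study's false-positive rate. Quoting only the upper part, from 18%, would require both links to be at least .3, and nothing in the documents establishes that.

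The point does not invalidate the design. It limits what may be said about a positive finding, and it is worth settling before the pattern is trained.

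**What to change.** In Section 6.0:

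1. State whether the cited pipeline includes cardiac or respiratory noise correction, and whether the Visit 2 pulse readings enter the fMRI model.
2. Prespecify, as a sensitivity analysis, a repeat of the full pattern training and testing with white-matter/CSF noise components (CompCor) in the first-level model. This needs only the images already planned.
3. Report the association of the pattern score with additional heart rate before and after adjustment for the Visit 2 in-scanner heart-rate response from the pulse oximeter.
4. Report prediction from white-matter and CSF voxels alone as a descriptive negative control. Do not make it a decision rule that grey matter must predict better: grey matter is more vascular, smoothing mixes tissues at their borders, and comparing two models at r of about .20 and N = 140 would have little power.
5. Use cardiac-phase regressors only if the oximeter waveform is available, which the protocol does not say.
6. Describe the pattern as neural only if prediction is materially retained with CompCor, with the meaning of material set in advance. Otherwise state that a physiological contribution cannot be excluded.

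**Cost.** Extra analysis and computing time, and some degrees of freedom per run. Steps 2 and 3 may remove true signal, so they should stand beside the primary analysis and not replace it. With no respiration recording named for the scanner, breathing-related signal would be addressed mainly through CompCor.

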
Brain-imaging studies of stressor-evoked cardiovascular reactivity. Recent meta-analyses have identified core components of a broad network of forebrain systems involved stressor-evoked changes in cardiovascular activity^{25,30-33}. These forebrain areas functionally interact with one another to modulate visceromotor and viscerosensory functions of cell groups within areas that govern and monitor autonomic and neuroendocrine outflow to the heart and blood vessels in coordination with behavioral actions and motivated dispositions to act³⁴⁻³⁶. Recent studies address previous limitations in stressor-evoked neuroimaging research by examining how patterns of responses, rather than voxel-by-voxel analyses, predict the likelihood of a certain magnitude of cardiovascular response^{37,38}. Using multivariate and cross-validation methods allows for more rigorous statistical testing and more generalizable results that could identify a brain phenotype that reflects CVD risk^{38,39}. Although it is the metabolically-disproportionate, stressor-evoked, cardiovascular reactions that are thought to most closely link with pathophysiological changes in vulnerable individuals, previous work in the field has only examined the neural correlates of stressor-evoked cardiovascular changes (i.e., cardiovascular reactivity)^{9,25,37,40-42}. This study will be the first study to directly test the hypothesis that metabolically-disproportionate, stressor-evoked, cardiovascular reactions are associated with ‘visceral prediction’ errors²⁸.

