2.0 STUDY OBJECTIVES

The main objectives of this study are to examine cardiovascular, metabolic, and neural responses to acute psychological stress. Additionally, the long-term goal of the study is to identify the multivariate pattern of stressor-evoked brain activity that reliably predicts individual differences in metabolically excessive responses to acute psychological stress.

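### Section 6 tests the brain pattern against responses other than the hypothesised additional heart rate, and N = 140 does not give the stated 80% power at r = .20

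*Combined protocol and SAP*

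**What the plan says.** Section 6 uses machine learning to produce "a multivariate pattern (3D regression weight map) that relates to heart rate and metabolic responses to stress". It then states: "The study will then test if this generated multivariate pattern can reliably predict cardiovascular and metabolic responses to stress". This is the only hypothesis test in the section. Reactivity is defined there as the stress value minus the baseline value, and additional heart rate is not mentioned.

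Other sections name a narrower target:

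- Section 2 gives the long-term goal as a pattern "that reliably predicts individual differences in metabolically excessive responses to acute psychological stress".
- The Section 4 rationale hypothesises that a pattern "will be able to predict the magnitude to which cardiovascular responses to stress are excessive of metabolic demand".
- The Section 4 account of Visit 2 says the imaging data are "required to develop multivariate analyses to predict metabolically excessive responses (i.e., additional heart rate").
- The Section 4 account of Visit 1 measurements says how additional heart rate is computed. Each person's own regression linking oxygen consumption and heart rate, fitted to rest and graded exercise, gives a predicted heart rate. This is subtracted from the observed one.

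On sample size, Section 6 takes a between-subjects correlation of about .20 from published pattern-prediction work and says that, "with alpha set at .05 and power = .80, it is estimated we will need a sample of at least" 140. It does not give the sidedness of the test, the participants on whom the map is evaluated, or how the p-value is obtained. Section 1 says: "Using multivariate and cross-validation methods allows for more rigorous statistical testing and more generalizable results". Section 6 does not carry that into a stated scheme.

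**The concern.** The two halves of the document do not describe the same test. The background and design sections justify the study by the gap between ordinary cardiovascular reactivity, which they say earlier imaging work has already examined, and metabolically disproportionate reactivity, which they say it has not. If the analysis relates brain activity to heart rate and metabolic responses as Section 6 reads, it could repeat the earlier kind of study and leave the new hypothesis untested. An analyst working from Section 6 could also choose among several responses after seeing the data.

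The power statement belongs to this same test. If 140 does not give 80% at the quoted effect, a null result would be read with more confidence than the design supports. The shortfall grows if some participants are set aside for testing.

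**Working it through.** **Outcome.** Write a person's exercise regression as predicted HR = a + b × VO2. By the Section 4 definition,

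additional HR = observed HR − (a + b × VO2).

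The change from baseline to stress in additional HR is therefore ΔHR − b × ΔVO2, with b specific to the person. Section 6 defines only differences of the form ΔHR (or ΔVO2). The two agree for everyone only if ΔVO2 is zero for everyone.

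| Place | Target of the pattern |
|---|---|
| Section 2 | metabolically excessive response |
| Section 4, rationale | response beyond metabolic demand |
| Section 4, Visit 2 | additional heart rate |
| Section 6, building the map | heart rate and metabolic responses |
| Section 6, testing the map | cardiovascular and metabolic responses |

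**The plan's own sample size.** Inputs from Section 6: r = .20, alpha = .05, power = .80. Sidedness is not stated, so both are shown. By Fisher z, N = ((z_alpha + z_power) / atanh(r))² + 3, with atanh(.20) = .2027.

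- Two-sided: ((1.960 + 0.842) / .2027)² + 3 = 194.
- One-sided: ((1.645 + 0.842) / .2027)² + 3 = 154.

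A noncentral-t calculation gives 191 and 150. The stated 140 is not reproduced at r = .20. Solving for the correlation detectable with 80% power, tanh((z_alpha + z_power) / √137) is .235 two-sided and .209 (about .21) one-sided.

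**Power at r = .20.** Power = Φ(atanh(.20) × √(n − 3) − z_alpha), where n is the number of participants in the test.

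| Participants in the test | Two-sided | One-sided |
|---|---|---|
| 140 (all) | 66% | 77% |
| 70 (half held out) | 38% | 51% |
| 47 (a third held out) | 27% | 38% |

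For all 140 two-sided: .2027 × 11.705 − 1.960 = 0.413, and Φ(0.413) = .660.

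Section 4 also says: "The same 150 participants will come to the VINS 17 CoE to engage in a functional magnetic resonance imaging protocol". That conflicts with the 140 in Sections 3.1 and 6. At 150 the power is 69% or 79%, so the conflict does not explain the gap.

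**Cross-validation.** No closed form applies, and the plan names no learner, so these figures come from simulation under assumptions: N = 140, ten folds, one-sided 5% permutation test, mainly regression on 3 to 20 image components. The answer turns on what .20 means.

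- If .20 is the accuracy in new people of a map trained on nine tenths of the sample (126), power is roughly 50-67%.
- If .20 is the average cross-validated correlation itself, power is roughly 60-83%.

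In simulations with no true relation, the pooled cross-validated r was not centred on zero. Its mean ran from −.18 to −.02 by learner. The chance of exceeding .166, the ordinary two-sided 5% cutoff at n = 140, ran from 0.1% to 5.9%, against a nominal 2.5%. The ordinary correlation table is therefore not a safe reference for it.

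**The case against.** **The outcome is named.** This is a combined protocol and SAP, and Section 4 both names additional heart rate and says how to compute it. Heart rate and metabolic responses could be shorthand for its two ingredients. Section 1 adds that psychological stress leaves predicted heart rate at its resting level, in which case the change in additional heart rate would equal the change in heart rate. What stands is that the target exists in the document, so the remedy is to reconcile the sections. A reader might infer that no outcome was ever specified; the documents do not support that. The shorthand reading is generous, however. Section 6 treats the responses as plural and gives no step that combines them. The Section 1 remark concerns the general pattern, whereas the analysis is about differences between individuals, and the study is justified by the distinction.

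**The effect is only approximate.** With a one-sided test and r = .21, Fisher z gives exactly 140. This is fair, but neither the sidedness nor .21 is stated, and at the quoted value neither version reaches 80%. On the more favourable reading of .20, some learners do reach 80% under cross-validation. The plan does not say that this is its basis.

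**The pattern may not be the main analysis.** Section 2 calls it a long-term goal, and Section 6 attaches its main analyses to averages at rest and under stress. Even so, the sample size rests on the pattern test.

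**Stronger readings.** A reader might infer that the map will be fitted and tested on the same people, because there is one cohort and no stated split. No section says so, and Section 1 points the other way. If it were done, the false-positive rate would depend on the learner, from 1-3% under a heavy L1 penalty through 28% for unpenalised regression on three components to 100% for whole-image ridge. A reader might also infer an inflated family-wise error from the plural responses, but the plan lists no set of tests from which to calculate one.

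**Conclusion.** Two faults stand in Section 6's only hypothesis test, and they should be corrected before the data are analysed.

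First, the outcome tested is not the outcome hypothesised. This follows from the text alone and needs no assumption.

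Second, the stated power does not follow from the stated inputs: 66% or 77% in place of 80% for an ordinary correlation of .20 on all 140 participants, and 38% or 51% with half held out. These figures assume a simple correlation, complete data and a true value of .20. The cross-validated ranges also depend on assumed learners and image structures, so they indicate order of magnitude only.

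The missing evaluation scheme and p-value method are a gap in detail, since out-of-sample testing is probably intended. They do not show an invalid analysis. The power result does not show that the study must enrol more people.

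**What to change.** In Section 6:

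1. Name additional heart rate, computed as in Section 4, as the single primary outcome of the pattern test, with other responses secondary. Section 4 computes it at baseline and during the MSIT, so say whether the stress value or the change is used.
2. State whether the test is one- or two-sided, and restate power at N = 140 for the scheme used, saying whether .20 is accuracy in new people or a cross-validated correlation. Reconcile the 140 with the 150 in Section 4.
3. As clarification, state that the map is evaluated out of sample, with every data-dependent step inside the training data. If cross-validation is used, take the p-value from permutation of the whole procedure. A hold-out set is also valid and can use the ordinary table, at lower power.

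The cost is SAP wording and computing time, with no new data, visits or enrolment. The downside is a stated power that will usually fall below 80%.
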